| 0.950 | 500 | 0.078 | 0.250 | 0.213 | 0.291 |
| 0.950 | 500 | 0.089 | 0.500 | 0.455 | 0.545 |
| 0.950 | 500 | 0.089 | 0.520 | 0.475 | 0.564 |
| 0.950 | 500 | 0.072 | 0.800 | 0.762 | 0.834 |
| 0.950 | 500 | 0.065 | 0.850 | 0.815 | 0.880 |

- Confidence level is the proportion of CIs (constructed with this same confidence level, sample size, etc.) that would contain the population proportion.
- N is the size of the sample draw from the population.
- Width is the distance from the lower limit to the upper limit.
- Actual width is the value of the width that is obtained from the procedure.
- Proportion (P) is the assumed sample proportion.
- Lower Limit is the lower limit of the CI.
- Upper Limit is the upper limit of the CI.

Using an estimate of 20% of patients being lost to follow-up, the plan will be to increase recruitment up to 625 patients to meet the target sample size of 500. It is also anticipated that in some patients, the viral load in samples collected at days 7, 14, and 28 (+/-2 days) will be too low for determination of the variable of interest. While undetectable viral load is a goal for treatment, this would further reduce the number of patients contributing to the assessment of the primary endpoint. Nonetheless, there remains adequate precision if

there are fewer patients contributing to analyses at day 7, for example (e.g. if there were 400 patients with a detectable viral load and 50% had AA changes that meet the criteria of interest, then the precision would be 95% CI 45.0-55.0%).

As a sentinel surveillance study, the aim will be to collect 500 (and up to 625) patients over the course of a year across the GB to meet the target sample size. Flexible enrolment caps per site and per month may be considered. The aim is to ensure continuous enrolment with appropriate geographical representation over the 12-month study period, to reflect the fast evolving COVID-19 pandemic. In addition, the target sample size will be re-assessed after the first 200-300 patients are enrolled in regard to progression towards achieving the primary objective, with the potential to decrease or increase the target number accordingly.

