4.2 Study Design

This is a phase IV, prospective cohort study amongst IC non-hospitalised patients treated with sotrovimab as part of standard clinical care to monitor the emergence of SARS-CoV-2 spike viral variants.

Patients will be followed for 28 days from the time they received sotrovimab treatment (index date (D0)) in one of the clinical sites. Data and samples will be collected following the schedule below (see also [Table 1](#))

Figure 1

- Non-hospitalised patients who are being treated with sotrovimab as part of standard of clinical care will be screened and enrolled if eligible (Day 0 = baseline). Informed consent, patient characteristics (demographic and clinical), and treatment history (related to COVID-19 and underlying diseases) will also be recorded at Day 0.
- Baseline nasal/oropharyngeal swab sample will be collected on site, as per protocol, under supervision after training and sent to the central analytical laboratory.
- Follow-up nasal/oropharyngeal swab samples (Day 7, 14 and 28 (+/- 2 days)) will be collected by the patients using home test kits or by healthcare professionals (HCP) in case of hospitalisation, as per protocol, with samples sent to the central analytical laboratory.

This document is confidential.

- Sequencing analyses will be conducted on all SARS-CoV-2 positive nasal/oropharyngeal swab samples that meet the threshold criteria for the sequencing assay.

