8.2 Key Definitions

End of Study (EOS)

The EOS is defined as the date the last participant completes the last visit as shown in the Schedule of Activities in [Section 4.8](#).

Study day

Event date can be adverse events, labs, or any other assessments during the study.

If the event date \geq date of first dose of sotrovimab, study day = event date – date of first dose of sotrovimab + 1.

If the event date $<$ date of first dose of sotrovimab, study day = event date – date of first dose of sotrovimab.

Baseline Value

Baseline value will be defined as the last non-missing value recorded prior to sotrovimab administration or as close as possible to the end of sotrovimab infusion.

Retrospective collection of baseline data with the patient or directly with patient HCP will be conducted when not possible at Day 0. In all cases baseline is defined to be Day 0.

Change from Baseline (CFB)

CFB = Post-baseline value – Value at baseline

Treatment Emergent

Treatment emergent amino acid substitutions include subjects where baseline and post-baseline records exist.

Treatment emergence for consensus will include baseline records of allelic frequency $>5\%$ and post-baseline $>50\%$ as thresholds, whereas treatment emergence for minority will include baseline records of allelic frequency $>5\%$ and post-baseline $>5\%$ as thresholds.

Consensus sequence is defined as allelic frequency $>50\%$ and minority species with allelic frequency $>5\%$.

Lower Limit of Detection (LLOD)

LLOD of the assay is defined as 453 copies/mL (equivalent to Ct=38).

Lower Limit of Quantification (LLOQ)

LLOQ of the assay is defined as 1570 copies/mL (equivalent to Ct=36.18).

Viral load Negatives

The threshold to declare a viral load negative is the LLOD.

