- AA changes in the SARS-CoV-2 spike consensus sequences from baseline in samples where viral load is insufficient for >5% allelic frequency analysis but sufficient to generate consensus level sequencing data

For the above endpoints, Baseline and post-baseline (Day 7, 14 and 28 (+/-2 days)) AA substitutions will be summarized by showing the counts and percentages of patients in spike and epitope substitutions separately for Minority species (>5% allelic frequency) as well as consensus sequence (>50% allelic frequency).

Treatment emergent AA substitutions in spike as well as epitope for minority species and consensus sequence would be listed separately.

A similar baseline and post-baseline AA substitutions summary were presented by VOC/VUI variants for the interim but will not be included in the final analysis..

Data listings will be provided for all the baseline and post-baseline AA substitutions in spike as well as epitope for minority species and consensus sequence separately.

- Viral load

Absolute and change from baseline viral load summaries will be based on Safety and Virology population respectively on log10 copies/mL.

An overall summary of viral load (log10 copies/mL) with actual values and change from baseline values of viral load as well as by Day 0, Day 7, 14 and 28 (+/-2 days) using descriptive statistics will be displayed and presented graphically over time.

In addition, viral load (log10 copies/mL) with actual values and change from baseline values will also be summarized by VOC/VUI variants, and for Epitope Substitutions by Residue and presented graphically over time. Also, individual subject profile plots of viral load by VOC/VUI will be graphically presented based on viral load imputed values.

.A summary of viral load (log10 copies/mL) with actual values using descriptive statistics will be presented for the subset of subjects who had missing viral load at Baseline, and separately for the subset of subjects who had a viral load available at Baseline.

Listings will be provided for all viral load data as well as a separate listing including only epitope substitution.

This document is confidential.

- **Viral Rebound**

A subject has experienced a virologic rebound when following conditions are met:

If subject is in the safety population and:

- Viral load increases $>1 \log_{10}$ copies/mL at any point in time following any previous sample.
OR

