Table	1.162	Summary of Absolute Viral Load (log 10 copies/mL) as measured by qRT-PCR from Nasal/oropharyngeal swabs for Subjects with missing Baseline Viral Load	Safety	Interim, Final
Table	1.163	Summary of Absolute Viral Load (log 10 copies/mL) as measured by qRT-PCR from Nasal/oropharyngeal swabs for Subjects with Baseline Viral Load	Safety	Interim, Final
Table	1.164	Summary of Change from Baseline in Viral Load (log 10 copies/mL) as measured by qRT-PCR from Nasal/oropharyngeal swabs	Virology	Interim, Final

This document is confidential.

Table	1.171	Summary of Absolute Viral Load (log 10 copies/mL) as measured by qRT-PCR from Nasal/oropharyngeal swabs by Variant of Concern (VOC)/ Variant Under Investigation (VUI)	Safety	Interim, Final
Table	1.172	Summary of Change from Baseline in Viral Load (log 10 copies/mL) as measured by qRT-PCR from Nasal/oropharyngeal swabs by Variant of Concern (VOC)/ Variant Under Investigation (VUI)	Virology	Interim, Final
Table	1.18	Proportion of subjects with undetectable viral load as measured by qRT-PCR from Nasal/oropharyngeal swab through Day 28	Safety	Interim, Final
Table	1.19	Summary of Proportion of Epitope substitutions at Baseline, Post-Baseline by VOC/VUI - Consensus Sequence (Allelic frequency >50%)	Safety	Interim
Table	1.20	Summary of Proportion of Treatment Emergent Epitope substitutions by VOC/VUI - Consensus Sequence (Allelic frequency >50%)	Safety	Interim
Table	1.21	Summary of Proportion of Epitope substitutions at Baseline, Post-Baseline by VOC/VUI - Minority species (Allelic frequency >5%)	Safety	Interim
Table	1.22	Summary of Proportion of Treatment Emergent Epitope substitutions by VOC/VUI - Minority species (Allelic frequency >5%)	Safety	Interim
Table	1.231	Summary of Absolute in Viral Load (log 10 copies/mL) as measured by qRT-PCR from Nasal/oropharyngeal swabs for Epitope Substitutions by Residue	Safety	Interim, Final
Table	1.232	Summary of Change from Baseline in Viral Load (log 10 copies/mL) by Baseline, Post-Baseline Epitope substitution (>=3 subjects)	Virology	Interim, Final
Table	1.241	Summary of Absolute in Viral Load (log 10 copies/mL) by Treatment-Emergent Epitope substitution (>=3 subjects)	Safety	

This document is confidential.

				Interim, Final
Table	1.242	Summary of Change from Baseline in Viral Load (log 10 copies/mL) by Treatment-Emergent Epitope substitution (>=3 subjects)	Virology	Interim, Final
Table	1.25	Summary of Clinical Outcomes	Completer (IA) Safety (FA)	Interim, Final

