Table	1.46	Summary of Proportion of Subjects with Amino Acid Substitutions in the Spike protein for Any Substitutions – Minority species (Allelic frequency >5%)	Safety	Final

This document is confidential.

Table	1.47	Summary of Proportion of Subjects with Treatment-emergent Amino Acid Substitutions in the Spike protein for Any Substitutions– Consensus Sequence (Allelic frequency >50%)	Safety	Final
Table	1.48	Summary of Proportion of Subjects with Treatment-emergent Amino Acid Substitutions in the Spike protein for Any Substitutions– Minority species (Allelic frequency >5%)	Safety	Final
Table	1.49	Summary of Absolute Viral Load (log 10 copies/mL) as measured by qRT-PCR from Nasal/oropharyngeal swabs in subjects with clinical outcomes	Safety	Final
Table	1.50	Proportion of subjects with undetectable viral load as measured by qRT-PCR from Nasal/oropharyngeal swab through Day 28 in subjects with clinical outcomes	Safety	Final
Table	1.51	Summary of Proportion of Amino Acid Substitutions at Baseline and Post-Baseline in Spike protein - Consensus Sequence (Allelic frequency >5%) in subjects with clinical outcomes	Safety	Final

15. Index of Figures

Figures	List of Interim and Final Reports	Population	Analysis
1.1	Mean Change from Baseline of Viral Load Log10 copies/mL	Virology	Interim, Final
1.2	Median Viral Load Log10 copies/mL by VOC/VUI	Safety	Interim, Final
1.3	Median viral load Log10 copies/mL over time of Epitope Substitution by Residue	Safety	Interim, Final
1.4	Individual subjects profile plot of viral load Log10 copies/mL by VOC/VUI	Safety	Interim, Final
1.5	Kaplan-Meier Plot for All-Cause Hospitalization by VOC/VUI subvariants –	Safety	Interim

This document is confidential.

16. Index of Listings

Listings		List of Interim and Final Reports	Population	Analysis
Listing	1.1	Subject Disposition	Screened	Interim, Final
Listing	1.2	Demographics and Baseline Characteristics	Safety	Interim, Final
Listing	1.3	Listing of all Baseline and Post-baseline Spike protein Amino Acid Substitutions – Minority species (Allelic frequency >5%)	Safety	Interim, Final
Listing	1.4	Listing of all Baseline and Post-baseline Spike protein Amino Acid Substitutions – Consensus sequence (Allelic frequency >50%)	Safety	Interim, Final
Listing	1.5	Listing of all Baseline and Post-baseline Epitope Amino Acid Substitutions – Minority species (Allelic frequency >5%)	Safety	Interim, Final

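### Viral load by treatment-emergent epitope substitution (Tables 1.241/1.242) is confined to patients whose virus stayed sequenceable after baseline, so it will look higher than the overall summaries even if the substitution has no effect

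*SAP*

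**What the plan says.** SAP 10.2, under viral load, plans actual values and change from baseline that "will also be summarized by VOC/VUI variants, and for Epitope Substitutions by Residue and presented graphically over time". That sentence does not say whether the substitutions are baseline or treatment-emergent. The SAP's Index of Tables does, for two tables planned at both interim and final:

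- Table 1.241 (Safety Set): "Summary of Absolute in Viral Load (log 10 copies/mL) by Treatment-Emergent Epitope substitution (>=3 subjects"
- Table 1.242 (Virology Set): "Summary of Change from Baseline in Viral Load (log 10 copies/mL) by Treatment-Emergent Epitope substitution (>=3 subjects"

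Three related displays are less specific. Table 1.231 is by residue, Table 1.232 by baseline and post-baseline substitution, and Figure 1.3 is titled "Median viral load Log10 copies/mL over time of Epitope Substitution by Residue".

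Two rules decide who can be classed as emergent. SAP 4.2: "Sequencing analyses will be conducted on all SARS-CoV-2 positive nasal/oropharyngeal swab samples that meet the threshold criteria for the sequencing assay". SAP 8.2: "Treatment emergent amino acid substitutions include subjects where baseline and post-baseline records exist".

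The overall summaries (Table 1.161 on the Safety Set, Table 1.164 on the Virology Set) carry no such condition. On detection, SAP 8.2 states "LLOD of the assay is defined as 453 copies/mL (equivalent to Ct=38", and SAP 8.3 replaces post-baseline values below that limit by half of it.

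**The concern.** The emergent groups are formed using post-baseline viral load, and post-baseline viral load is then what is tabulated for them. A patient who drops below the sequencing threshold before Day 7 and stays there can never be shown to have an emergent change, whatever happened to the virus. That patient is absent from Tables 1.241/1.242 and present, at a low value, in the overall tables.

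The study exists because treatment might select virus with reduced susceptibility to sotrovimab, and its interim and final reports go to the regulator. Higher viral load in patients with an emergent epitope change is easily read as virological failure caused by the substitution. This selection produces that pattern with no such effect.

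**Working it through.** **1. The SAP's own substituted values (SAP 8.2, 8.3).**
- Below LLOD: 0.5 × 453 = 226.5 copies/mL; log10 = 2.355, stated as 2.36. Reproduced.
- Between LLOD and LLOQ: 1570 − 0.5 × (1570 − 453) = 1011.5 copies/mL; log10 = 3.005, stated as 3.00. Reproduced.

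A sample showing an emergent substitution is positive, so it counts as at least 3.005. A cleared sample counts as 2.355. The difference, 3.005 − 2.355 = 0.65 log10, is the minimum gap at that visit between a sample showing a substitution and a cleared one. It needs no kinetic assumption.

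**2. Size at Day 7, first set of assumptions.** All inputs are assumed: baseline mean 6.5 (SD 1.5) log10; 7-day fall mean 2.5 (SD 1.0); emergence in 20% of sequenced patients, independent of viral load; SAP 8.3 substitutions applied; 400,000 simulated patients.

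| Sequencing threshold (log10) | Emergent group | All baseline-positive | Gap |
|---|---|---|---|
| 3.5 | 5.13 | 4.18 | 0.95 |
| 4.0 | 5.44 | 4.18 | 1.26 |
| 5.0 | 6.12 | 4.18 | 1.94 |

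Patients sequenced at Day 7 without a change have the same mean as the emergent group, to within 0.01.

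**3. All visits, second set of assumptions.** Baseline mean 6.5 (SD 1.2); median decline 0.30 log10/day (log-SD 0.6); noise SD 0.5; threshold 3.2 log10; 20% emergence per sequenceable sample, independent of viral load and clearance.

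| | Emergent | Whole Virology Set | Difference |
|---|---|---|---|
| Mean, Day 7 | 5.33 | 4.28 | 1.05 |
| Mean, Day 14 | 3.93 | 3.18 | 0.75 |
| Mean, Day 28 | 2.77 | 2.53 | 0.24 |
| Change, Day 7 | −1.62 | −2.22 | smaller fall |
| Change, Day 14 | −3.02 | −3.33 | smaller fall |
| Change, Day 28 | −4.18 | −3.97 | larger fall |

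Day 28 change reverses because the emergent group starts higher (6.95 against 6.51) and both groups approach the 2.36 floor.

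I then varied the threshold (2.66 to 4.0), emergence (9% or 20%, the epitope percentages quoted in Protocol 8.5) and median decline (0.20 to 0.45). The Day 7 excess over the whole Virology Set runs from 5.61 − 4.91 = 0.70 to 5.71 − 4.29 = 1.42 log10. Against patients outside the emergent group it is 0.98 to 1.63 at Day 7 and 0.75 to 1.23 at Day 14.

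**4. Does a landmark remove it?** The inputs are those of step 3. Take patients sequenced at baseline and Day 7, and split them by emergence at Day 7. Mean viral load is 3.53 against 3.53 at Day 14, and 2.61 against 2.61 at Day 28. Restricting to patients with any post-baseline sequence, without a landmark, is not enough: 27% of emergent against 45% of non-emergent patients are undetectable at Day 14.

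**5. Does the same comparator suit baseline-substitution groups?** No. With the inputs of step 2, patients sequenced at baseline average about 4.2 to 4.5 log10 at Day 7. Patients sequenced at Day 7 average 5.13 to 6.13. Comparing the first with the second makes baseline carriers appear to clear faster, by about 0.9 to 1.7 log10, again with no true effect.

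**The case against.** The strongest reply is that the study is descriptive. No contrast between epitope groups is planned, and viral load by substitution is not among the objectives in SAP 3 or the endpoints in SAP 6. The selection is also partly disclosed. Protocol 8.5 warns, for part of the cohort, that "the viral load in samples collected at days 7, 14, and 28 (+/-2 days) will be too low for determination of the variable of interest", Protocol 8.9 notes that changes below the assay's detection threshold will be missed, and Table 1.43 describes who was sequenced across visits. This limits the weight of the point. It does not answer it, because none of these passages applies the selection to the viral-load displays. Protocol 8.9's caveat about lacking an untreated group concerns sotrovimab's role, whereas this bias lies within the treated cohort.

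A reader might infer more than the documents support:

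- **That every epitope display is affected.** Tables 1.231/1.232 and Figure 1.3 are not stated to be treatment-emergent. A substitution present at baseline needs no later sequence.
- **That patients who clear never appear.** A patient sequenced at Day 7 who clears later is in Tables 1.241/1.242. In the main scenario of step 3, 27% of the emergent group is undetectable at Day 14 and 75% at Day 28.
- **That falls look smaller at every visit.** Step 3 shows the reverse at Day 28.
- **That no comparator exists.** The index gives titles, not rows. The table shells are a separate document not available here and may hold a comparator row or footnote. The SAP text and index simply do not require one.

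**Conclusion.** The point holds for Tables 1.241 and 1.242, and for any group in Tables 1.231/1.232 or Figure 1.3 that is defined by a post-baseline substitution. It does not hold for baseline-defined groups. The selection itself follows from SAP 4.2 and 8.2 without modelling.

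The direction is higher absolute viral load at each visit examined and smaller falls at Days 7 and 14. The size is illustrative, because the sequencing threshold and viral kinetics are assumed: roughly 1 to 2 log10 at Day 7, with a full range of 0.70 to 1.94 against the overall summary. The comparison with the overall tables is one a reader would make, not one the SAP specifies. This is a worthwhile, low-cost improvement to secondary displays, and it leaves the primary endpoints untouched.

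**What to change.** 1. In Tables 1.241/1.242, and for any post-baseline-defined group in Tables 1.231/1.232 and Figure 1.3, add a landmark comparator: patients with evaluable sequences at baseline and at the same post-baseline visit, and no treatment-emergent epitope substitution at that visit. Evaluability should be judged at the same allelic-frequency level in both groups.
2. Compare viral load only after the landmark: Days 14 and 28 for a Day 7 landmark, Day 28 for a Day 14 landmark. Describe substitutions first detected at Day 28 without a later comparison.
3. Compare baseline-substitution groups with patients sequenced at baseline who had no epitope substitution, not with the post-baseline-sequenced group.
4. State in Tables 1.231/1.232 and Figure 1.3 whether each group is defined at baseline or post-baseline.
5. Footnote that emergent groups must not be compared with the whole Safety or Virology Set.

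The cost is SAP and shell wording, landmark flags and a few extra rows or lines, all from data already held. The drawback is small groups at the later landmark, some of which may fall under the three-subject minimum used in these tables.

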7.2 Safety Set

The Safety Set (SS) will include all participants who were enrolled and exposed to study intervention.

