8.3 Missing Data

For participants who are withdrawn from the study prior to the end of the study, all data collected up to the point of discontinuation will be used for analysis.

Imputation will be performed on post-baseline viral loads depending on the viral load results as below:

This document is confidential.

Viral loads that are missing or less than the LLOD (453) will be imputed as $0.5 \times \text{LLOD} = 0.5 \times 453 = 226.5$ copies/ml = 2.36 log10c/ml.

Viral loads that are above the LLOD but lower than the LLOQ (1570) will be imputed as $\text{LLOQ} - 0.5 \times (\text{LLOQ} - \text{LLOD}) = 1570 - 0.5 \times (1570 - 453) = 1011.5$ copies/ml = 3.00 log10c/ml.

Possible VL results	LLOD	LLOQ	Reported in the listings as:	Imputation for analysis:
Missing (as Ct>45)	453	1570	NEG	Half LLOD = 226.5 copies/ml = 2.36 log10c/ml
<LLOD, e.g. 400	453	1570	NEG	Half LLOD = 226.5 copies/ml = 2.36 log10c/ml
Between LLOD and LLOQ, e.g. 1000	453	1570	<1570	LLOQ - 0.5*(LLOQ-LLOD) = 1011.5 copies/ml = 3.00 log10c/ml
>LLOQ, e.g 2000	453	1570	Numeric result	None – use numeric result

For calculating age, birth date will be imputed as follows:

For all subjects, the missing date and month will have this imputed as '30th June'.

Birth date will be presented in listings as 'YYYY'.

Completely missing dates of birth will remain as missing, with no imputation applied. Consequently, the age of the subject will not be calculated and will remain missing.

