- Viral load becomes quantifiable after having been below the limit of quantification (LLOQ) or limit of detection (LLOD).

A table will be summarized with number of subjects who met viral rebound and will also list out their viral load information.

11. Safety

All safety analyses will be conducted using the safety population.

In this study, only events considered related to sotrovimab are collected and referred to adverse drug reactions (ADRs). Therefore, any reference to AE in subsequent sections indicates ADR, unless otherwise stated.

Safety will be assessed on the basis of reporting and analyzing of AE .

Only descriptive statistics will be produced.

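### The SAP 10.2 rebound rule requires no earlier on-study fall, so first rises after Day 0 count as rebound and are pooled with LLOQ crossings of under 1 log10

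*SAP*

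**What the plan says.** SAP 10.2 defines viral rebound for the safety population by two criteria joined by OR. Criterion 1 is a rise of more than 1 log10 copies/mL "at any point in time following any previous sample". Criterion 2 reads "Viral load becomes quantifiable after having been below the limit of quantification (LLOQ) or limit of detection (LLOD"). The output is described in one sentence: "A table will be summarized with number of subjects who met viral rebound and will also list out their viral load information". The indexes name it as Table 1.44, a cumulative proportion on the Safety Set for the final analysis, with Listing 1.27 for the individual values.

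The Safety Set (SAP 7.2) "will include all participants who were enrolled and exposed to study intervention". It carries no viral load condition. The Virology Set (SAP 7.3) does, requiring a baseline at or above the LLOD, but it is not used for rebound.

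SAP 8.2 states "LLOD of the assay is defined as 453 copies/mL (equivalent to Ct=38") and "LLOQ of the assay is defined as 1570 copies/mL (equivalent to Ct=36.18"). SAP 8.3 says "Imputation will be performed on post-baseline viral loads": negatives take half the LLOD, and results between the two limits take their midpoint. The sentence in SAP 8.3 speaks of missing values in general, while its table narrows this to "Missing (as Ct>45").

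The protocol does not define rebound, and rebound is not among the endpoints in SAP section 6.

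**The concern.** A reader of a table on viral rebound will take it to mean that the virus went down under observation and then came back. The rule does not require the first half of that. Day 0 is a scheduled sample and so can be the earlier sample. A patient still on the way up at treatment, or one with a poor or low Day 0 swab and a better Day 7 swab, is counted in the same way as a patient who cleared and relapsed.

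The two criteria also describe events of different size. Criterion 1 asks for a tenfold rise, while criterion 2 asks only that a reporting limit be crossed. SAP 10.2 does not ask for them to be shown apart. In a surveillance study of immunocompromised patients after an antibody, the proportion with rebound is likely to be quoted on its own, and as defined it can exceed the proportion with a fall followed by a rise.

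**Working it through.** **Inputs.** LLOD 453 and LLOQ 1570 copies/mL (SAP 8.2); analysis values for results below these limits (SAP 8.3); the two criteria (SAP 10.2).

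**Step 1: reproduce the SAP's analysis values.**
- Negative: 0.5 × 453 = 226.5 copies/mL; log10 = 2.36.
- Between LLOD and LLOQ: 1570 − 0.5 × (1570 − 453) = 1011.5 copies/mL; log10 = 3.00.

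Both agree with SAP 8.3.

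**Step 2: smallest rise that meets criterion 2.** The formula is log10(1570 / earlier value).
- After an LLOD-LLOQ result: log10(1570 / 1011.5) = 0.19.
- After a negative: log10(1570 / 226.5) = 0.84.

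Both are below the more than 1 log10 of criterion 1. Criterion 2 alone therefore admits results from 1570 up to 10 × 1011.5 = 10,115 copies/mL after an LLOD-LLOQ result, and up to 10 × 226.5 = 2,265 after a negative. SAP 10.2 does not say whether raw or imputed values are used. On raw values the distance from LLOD to LLOQ is log10(1570 / 453) = 0.54, so the conclusion is the same.

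**Step 3: apply the rule to illustrative patients.**

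| Day 0 | Day 7 | Day 14 | Rise (log10) | Criterion met | Fall seen on study first? |
|---|---|---|---|---|---|
| 4.5 log10 | 6.0 log10 | – | 6.0 − 4.5 = 1.5 | 1 only | No |
| 1,000 copies/mL | 2,000 copies/mL | – | log10(2000 / 1000) = 0.30 | 2 only | No |
| 6.0 log10 | <1570 | 1,700 copies/mL | log10(1700 / 1011.5) = 0.23 | 2 only | Yes |
| 5.0 log10 | NEG | 2,000 copies/mL | log10(2000 / 226.5) = 0.95 | 2 only | Yes |
| 6.0 log10 | NEG | 5.0 log10 | 5.0 − 2.36 = 2.64 | 1 and 2 | Yes |

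All five count as rebound. The first two show no fall on study.

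**Step 4: size of the crossing and the word rebound.** The fourth patient fell by 5.0 − 2.36 = 2.64 log10 and then became quantifiable. Had the Day 14 result been 2,300 copies/mL, the rise would be log10(2300 / 226.5) = 1.01 and criterion 1 would also be met. The difference between 0.95 and 1.01 rests on the half-LLOD placeholder, so a minimum rise should not decide whether this pattern is called rebound.

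**Step 5: untested samples.** If the SAP 8.3 sentence were followed rather than its table, an unreturned Day 7 swab would take 226.5. A Day 14 result of 3.5 log10 would then be a rise of 3.5 − 2.36 = 1.14 from a sample that was never tested.

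**The case against.** The rule is explicit and programmable, and no passage in either document says that rebound needs a prior fall or a fixed rise, so nothing is contradicted. This stands: the point concerns what the reported proportion means.

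A crossing criterion has a good reason to be categorical. Below the LLOQ there is no reliable measured value, and a fold-rise from there depends on a placeholder. This stands too. A reader might infer that criterion 2 breaches a 1 log10 standard of the SAP. It does not, because that figure belongs to criterion 1 alone. A reader might also say that the qualifying rise can be practically zero, for example 1569 to 1571 copies/mL. After baseline, SAP 8.3 lists the first of these as <1570 and analyses it as 1011.5, so 0.19 log10 is the smallest step on its analysis values.

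A Day 0 result below the LLOQ may follow a fall before enrolment, since Protocol 8.2.1 requires a positive test. That is possible, but the study did not observe it.

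The data would remain visible. Listings 1.27 and 1.131 and the profile plots in Figure 1.4 let a reader sort cases by hand. If Table 1.44 is cumulative by visit, its Day 7 entries can only be rises from Day 0. That layout is an inference from the title, and it would not isolate a first rise seen at Day 14 or 28. SAP 12.2.5.2 leaves denominator details to footnotes or programming notes, so the documents do not show that the denominator is wrong. The shells are a separate document (SAP 17.1) and could already contain a split, though SAP 10.2 does not ask for one.

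**Conclusion.** The point holds, with minor weight. Followed as written, SAP 10.2 counts first rises after Day 0, and first LLOQ crossings after a low Day 0 value, as virologic rebound. It also pools crossings from 0.19 log10 (after an LLOD-LLOQ result) or 0.84 log10 (after a negative) with rises above 1 log10. Those two figures assume that the SAP 8.3 analysis values are used for a post-baseline earlier sample.

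A reader might conclude that Table 1.44 will be materially inflated. The documents do not support that: they give no viral load distribution, so the number of affected patients cannot be derived. Nor is any endpoint, test or decision at risk. Rebound is descriptive and lies outside the protocol endpoints and SAP section 6. What is affected is how one reported proportion reads.

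**What to change.** In SAP 10.2 and Table 1.44, keep the Safety Set and the current total, and label the total as any qualifying rise. Then split it in two steps:

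- **(a) Observed fall or not.** A fall is observed if the sample from which the rise is measured is a tested post-baseline sample lower than an earlier tested on-study sample. A move to a lower reporting category (quantifiable, <1570, NEG) counts as lower. Everything else, including a rise from Day 0 or one with no earlier tested sample, is a rise without an observed fall.
- **(b) Within each group,** criterion 1 met versus LLOQ crossing only.

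A patient with several qualifying rises goes to the observed-fall group if any of them qualifies there, and then to criterion 1 if any rise in that group meets it. Use the word rebound for everyone in the observed-fall group, whichever criterion was met, and do not use it for first rises.

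Only tested samples should serve as earlier samples, so align the SAP 8.3 sentence with its table and leave out unreturned swabs. Split (b) also needs a stated value for a Day 0 result below the LLOQ, because SAP 8.3 imputes post-baseline values only. For example, a negative Day 0 followed by 3,000 copies/mL is a rise of log10(3000 / 226.5) = 1.12 from half the LLOD, but log10(3000 / 453) = 0.82 from the LLOD.

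Beside the full Safety Set, show how many patients had at least 2 tested samples (the minimum for any qualifying rise) and at least 3 (the minimum for a fall and then a rise).

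The cost is SAP wording, one derivation, four rows and two sample counts, all from data already in the collection plan. The downsides are a longer table and fewer patients in whom a fall and then a rise can be seen. A very small fall, or a false-negative dip, would still count as a fall. The split adds no size threshold for the fall, and the documents give none.
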